## III. Description of protocol methodology

### **Summary**

To meet our aims, we propose a 2,000-person two-arm, double-blinded randomized controlled trial in HCWs and other Chicagoland community adults at University of Chicago Medicine (UCM) and Rush University (RU) selected to ensure safe administration of low compared to moderate or high dose vitamin D that will randomize half the subjects to low dose vitamin D therapy (400 IU/day) and half to moderate (4,000 IU/day) or high (10,000 IU/day).

During the consent process, study participants will be able to choose between being randomized between the low versus high dose strategy or the low dose versus moderate dose strategy. Moderate and high dose treatment participants will be combined for analysis as described below. The moderate and high treatment doses were chosen with help from our clinical advisory committee because they are generally considered safe and potentially effective among persons who meet our inclusion criteria based on medical history and baseline laboratory values (normal calcium and PTH, and negative COVID-19 antibodies). The low dose was selected to ensure that all subjects had a high likelihood of a total vitamin D intake that met the recommended daily allowance (RDA). All patients will be informed of whether their baseline calcium and PTH are normal. Patients who are still eligible for study participation after initial testing will be asked prior to randomization whether they are still willing to participate to maximize retention and minimize dropout. After randomization, subjects will be instructed to pick up their 9-month supply of vitamin D at either UCMC or Rush University corresponding to their randomized, blinded dose. For those unable to pick up their bottles in-person, the UCM IDS pharmacy will mail the subject their bottle. We propose a 3 to 9-month study period, depending on when the subject was recruited, as described in the study timeline of Section IV. Subjects recruited after September 30th will participate in the intervention 6 months to align with study timeline and funding. Subjects enrolled between January 1, 2023 and March 31, 2023 will take the study drug until June 2023, so at least 3 and no more than 6 months. Chart review for subjects will occur for 12 months after the active intervention period has ended. This study timeline is further detailed in Tables 1-4 of Section IV in the currently approved protocol document. Adverse events, defined as hypercalcemia or unexplained increased falls in either study arm will prompt discontinuation of the study medication and further evaluation as reported in the monitoring section below.

[figure not shown]
On the advice of our Clinical Advisory Council faculty members, patients who test for PTH >85pg/dL but have calcium levels <10mg/dL and low vitamin D (<30ng/mL) will be eligible to continue in the study because those

who have elevated PTH, but low vitamin D and normal calcium likely have secondary hyperparathyroidism due to low vitamin D levels. However, since there is some risk that the PTH elevation in these patients is not due to low vitamin D, but instead primary hyperparathyroidism, we will check their calcium levels 30 days after they begin vitamin D supplementation and will follow the referral algorithm in the protocol should their calcium level become abnormal. Given this, we plan to reach out to subjects who have been previously disqualified but now meet the inclusion criteria to continue in our study to see if they still would like to participate. If they would like to, we will dispense them their randomized dose of vitamin D and follow up with calcium testing in approximately one month. Our exclusion criteria has therefore been modified to exclude those with  $\text{PTH} > 85 \text{ pg/dL}$  but with calcium  $\geq 10 \text{ mg/dL}$  and normal levels of vitamin D ( $\geq 30 \text{ ng/mL}$ ).

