### Procedures and Materials

Blood labs will be taken from subjects at intake, 3 months, 6 months and, if in the 9-month cohort, 9 months. If subjects are in the 2023 cohort (defined as recruited on or after January 1, 2023) blood labs will be taken from

subjects at intake, 3 months, and, if they are recruited in January or February 2023, they will have one final blood draw in June 2023. Labs for UCM subjects will be drawn at DCAM phlebotomy, River East phlebotomy, or Ingalls Hospital, depending on the location most convenient for the subject. Labs for Rush subjects will be drawn by [name] at his Rush lab.

Intake labs will measure baseline calcium and PTH levels, presence of COVID-19 antibodies, baseline vitamin D levels, and vitamin A levels. Where possible given constraints related to sample storage, analysis and available funding for free vitamin D measurement, vitamin D measurements will include free vitamin D levels measured by ELISA assay, as well as total vitamin D levels.

For Aim 7, Intake labs for UCM subjects will additionally measure vitamin D-binding protein (DBP), RAS components (Renin, Ang II, soluble ACE and ACE2), bradykinin, inflammation markers (IL-6, TNF- $\alpha$ , IL-1 $\beta$  and CRP), and SARS-CoV-2 antibodies against S-protein and N-protein.

Follow-up labs (excluding the final lab) will measure PTH levels, calcium levels, vitamin A levels for those who have high baseline vitamin A, and vitamin D levels for monitoring of the intervention's safety and outcomes, and COVID-19 antibodies for monitoring of the outcome. Records of these levels will be kept by the UCM and RU PIs and laboratories.

Final labs will measure calcium levels, vitamin D levels for monitoring of the intervention's safety and outcomes, and COVID-19 antibodies for monitoring of the outcome. Records of these levels will be kept by the UCM and RU PIs and laboratories. Final labs will not measure PTH levels. During the intervention period, our study monitors PTH levels for active participants, because primary hyperparathyroidism is a risk factor for vitamin D toxicity. Given that participants will no longer be taking study-provided vitamin D after their final lab draw, we do not believe it is medically necessary or an appropriate use of limited study resources to continue checking PTH levels with this final draw.

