The sample size was chosen to have at least 80% power to detect a 25% or larger decrease in the hazard of developing COVID-19 between study arms at  $p<0.05$  assuming a 30% baseline COVID-19 incidence rate over the study period, in line with the 3% per month incidence cited above.

*Individuals are eligible to enroll in the study if they:*

1. Are 18 years or older.
2. Live or work in the Chicagoland area (Illinois counties: Cook, Lake, McHenry, DuPage, Kane, Kendall, Grundy, Will, and Kankakee; Indiana counties: Lake and Porter).
3. Are interested in vitamin D as a potential preventive measure against COVID-19 in which they self-administer a daily dose of vitamin D during the 9-month study period.
4. Are willing to attend the laboratory for drop-in appointments at UChicago Medicine, Ingalls Hospital, or Rush University Medical Center every 3 months at up to 4 time points over up to a 9-month period for blood draws measuring COVID-19 antibodies, calcium, vitamin D and PTH levels.
5. Are willing to complete self-report measures at up to 4 time points over the course of up to 9 months by completing a 15-minute survey at intake by telephone or via web and 10-minute web-based follow-up surveys.

*Individuals are excluded from the study if they:*

1. Report being pregnant, planning to become pregnant, and/or report breastfeeding during the study period.
2. Report a history of chronic kidney disease, including a history of abnormal GFR and/or creatinine.
3. Report a history of hyperparathyroidism.
4. Report a history of increased falls.
5. Report a history of hypercalcemia.
6. Report a history of gastrointestinal absorptive disorders, including having undergone bariatric surgery.
7. Report a history of kidney stones (1 in past year or 2 in lifetime).

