8. Report already taking more than 400 IU of vitamin D daily as recommended by their health care provider, excluding multivitamins and excluding supplements that include vitamin D and calcium together, unless permission is received from the prescribing health care provider to participate. In this case, no more than 1,000 IU vitamin D may be taken daily in addition to the study medication and we would limit the subjects to participation in the low vs. moderate arm of the study, producing a maximum dose of 5,000 IU per day. We note that the NAM recommended a maximum dose of 4,000 IU per day without medical supervision based on evidence that 5,000 was safe and known uncertainty about the precision of dosing in 5,000 IU supplements available over the counter. However, since we are testing the dosage of our 4,000 IU supplements to high precision and these patients would be taking their original supplements with a labelled dose of 1,000 IU or less, we think that the combination of our 4,000 IU supplements and the patient's original supplement of up to 1,000 IU should not provide a maximum dose meaningfully above the 5,000 IU actual dose the NAM has considered safe for taking without medical supervision. We note further that we are measuring vitamin D levels and PTH in these patients regardless in this study. We do, however, have another study of vitamin D and COVID (IRB# 20-0847), in which we are not measuring these levels, for which it is more important to not substantially exceed NAM maximum level of 5,000 IU per day. The approach described here allows us to align the approach in these two studies.
9. Report taking D2.
10. Report a history of sarcoidosis.

11. Screen positive for hypercalcemia ( at UCM, defined as >10.4 mg/dL and at Rush, defined as >11.2 mg/dL) during the initial blood test.
12. Screen positive for hyperparathyroidism (PTH>85 pg/dL) during the initial blood test with calcium  $\geq 10$ mg/dL and normal levels of vitamin D ( $\geq 30$ ng/mL)
13. Have vitamin D levels of >100ng/mL at study start, or >250ng/mL during follow-up labs.
14. Are unwilling to provide blood samples during quarterly blood tests.
15. Are unwilling to take daily vitamin D.

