For our primary outcome of COVID-19 infection as measured by patient report of clinically confirmed COVID-19 (or viral PCR when available) and secondary outcomes of COVID-19 antibody seroconversion and disease severity (hospitalization, ICU stay, ventilator use, death), hazard models will be employed to assess the effect of each vitamin D dosing strategy on the outcome. We will first develop hazard ratios for between-group analyses on the primary outcome using log-rank tests, and then develop Cox proportional hazard models to model the hazard function on a set of covariates including but not limited to, moderate or high vitamin D dose, baseline vitamin D levels, age, gender, race, ethnicity, sun exposure, sleep habits, exposure of cohabitants, job type, and study site. We will also control for randomization date to adjust the underlying hazard function for COVID-19 prevalence over time. While our primary analysis will pool subjects randomized to either the moderate or high dose and compare them to low dose subjects, we will also perform secondary analyses comparing low to moderate and low to high and additional analyses that use post randomization vitamin D levels as time varying covariates. The design thus seeks to maximize potential to find statistically significant results between different dosages given uncertainty in subject willingness to be randomized to different doses. As noted above, the sample size was chosen to have at least 80% power to detect a 25% or larger decrease in the hazard of developing COVID-19 between study arms at  $p<0.05$  assuming a 30% baseline 10-month COVID incidence over the study period, in line with the 3% monthly incidence cited above. As finding that a higher dose has no effect or a paradoxical adverse effect on COVID incidence would both lead to use of a lower dose given even the small risks of higher dose vitamin D, Ruxson and Neuhauser would argue for use of a 1-sided test, resulting in 80% power to detect a 20% or larger decrease.

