- For individuals who have been enrolled in the study for more than one month, we will reach out to them individually via email using the Existing Subject email scripts to inform them that in light of vaccine prioritization to HCWs, we are expanding our recruitment to adults in Chicagoland communities to give them access to the possible of benefits of COVID-19 prevention with vitamin D. We will ask them if they would be willing to forward the FAQ sheet to their family members, friends, or others in their network who they think may be interested.
- For groups of HCWs who we have reached already with recruitment materials, we will follow up with those groups using the Community Listserv scripts and inform them that in light of vaccine prioritization to HCWs, we are expanding our recruitment to adults in Chicagoland communities to give them access to the possible of benefits of COVID-19 prevention with vitamin D. We will re-attach the FAQ sheet and ask them to forward it to those in their networks who they think might be interested in participating.
- For HCWs who we have not yet reached out to about participating in the study, we will use the Community listserv scripts to both ask them if they are interested and ask if they could share the information with those who may be interested in their networks.
- For individuals who have previously been disqualified at enrollment due to ever having a self-reported positive PCR test or a positive baseline antibody test, we will contact these individuals and ask if they are interested in enrolling. We will have these individuals enroll using the same processes for new subjects.

For community recruitment other than HCWs and the social networks of study participants, we will begin by leveraging existing community relationships to reach out to primary contacts at a variety of community organizations via phone or email. We will also recruit in Chicagoland neighborhoods, handing out brochures and/or flyers to local businesses.

For community recruitment, we use the "Joint Interest Form- RedCap" on iPads or laptops when we are recruiting. RCs, RAs and Americorps members, when a potential participant indicates interest in learning more about the study, will enter potential participant information into this form so they can be later followed up with by study teams. This will allow the study team to answer questions and, as applicable, conduct screening, in a private setting at a time convenient for the potential participant.

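### The protocol gives conflicting eligibility rules for people with prior COVID-19 or positive antibodies, and the primary analysis does not prespecify baseline infection status

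*Combined protocol and SAP*

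**What the plan says.** Three parts of the current text bear on whether someone who has had COVID-19 may enter.

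- **Section III, Summary.** The dose rationale refers to people who meet "inclusion criteria based on medical history and baseline laboratory values (normal calcium and PTH, and negative COVID-19 antibodies" (the bracket closes after the last word).
- **Section VIII.** There are five inclusion items and, under "Individuals are excluded from the study if they", fifteen exclusions. The laboratory exclusions concern calcium, PTH and vitamin D, for example "Have vitamin D levels of >100ng/mL at study start, or >250ng/mL during follow-up labs". No item concerns antibodies or past COVID-19.
- **Section XVII, community recruitment.** The bullet that opens "For individuals who have previously been disqualified at enrollment due to ever having a self-reported positive PCR test or a positive baseline antibody test" says these people will be contacted again, and then: "We will have these individuals enroll using the same processes for new subjects".

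On measurement, Section III, Procedures and Materials, states: "Intake labs will measure baseline calcium and PTH levels, presence of COVID-19 antibodies".

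On analysis, Section IX specifies a log-rank test and then a Cox model for reported, clinically confirmed COVID-19. The named covariates are the dose variables and "baseline vitamin D levels, age, gender, race, ethnicity, sun exposure, sleep habits, exposure of cohabitants, job type, and study site". The list is expressly open-ended, and randomisation date is added to allow for changing prevalence. Section IX names no stratum, subgroup, sensitivity analysis or at-risk set based on baseline infection status.

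**The concern.** An antibody-positive volunteer is ineligible on the Section III wording, not addressed by the numbered criteria, and actively sought under Section XVII. Only one of these can be the operating rule.

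Section XVII also shows that prior infection was once disqualifying and no longer is. The enrolled population was therefore widened on a factor likely to matter for the primary hazard, and the analysis section did not follow. Three things are at stake:

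- A strong baseline predictor is left out of the named model, which costs some power.
- If the effect differs by infection history, the pooled hazard ratio will understate the effect in never-infected people, and no planned analysis would show it.
- Someone antibody-positive at baseline cannot seroconvert, yet the seroconversion analysis has no stated at-risk set.

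**Working it through.** **1. The texts side by side.** Section III requires negative antibodies, Section VIII is silent, and Section XVII enrols people with a past positive PCR or antibody test. Sections VIII and XVII are compatible with each other. The Section III parenthesis is the outlier and is probably a leftover. None of the three is an amendment log. The mixing of infected and never-infected people follows from the Section XVII rule; the contradiction in wording does not itself cause it.

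**2. The plan's own power figure.** Inputs from Sections VII to IX: 2,000 people allocated 1:1, control incidence 30%, hazard ratio 0.75, p<0.05 read as two-sided.

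- Treated incidence = 1 − 0.70^0.75 = 0.2347.
- Events = 1,000 × (0.30 + 0.2347) = 535.
- Power (Schoenfeld) = Φ(√(535/4) × |ln 0.75| − 1.96) = Φ(3.33 − 1.96) = 91.4%.
- 80% power needs 380 events, or about 1,422 people.

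The claim of at least 80% power is reproduced, with slack.

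**3. Adding previously infected people.** The documents give neither their share (f) nor their hazard relative to never-infected people (r). Both are assumptions here: f = 20–40%, r = 0.2–0.5. The 30% incidence is taken to apply to the never-infected.

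- Control survival S0 = (1 − f) × 0.7 + f × 0.7^r.
- Treated survival S1 = (1 − f) × 0.7^0.75 + f × 0.7^(r·h), where h = 0.75 for a common effect and h = 1 for no effect in the previously infected.
- Events = 1,000 × (2 − S0 − S1). Pooled hazard ratio = ln S1 / ln S0. Power is as in step 2.
- Stratified power (common effect) uses the same events with a hazard ratio of 0.75.

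Example, f = 0.4, r = 0.2, common effect: S0 = 0.42 + 0.4 × 0.9311 = 0.7925. S1 = 0.6 × 0.7653 + 0.4 × 0.9479 = 0.8383. Events = 1,000 × (0.2075 + 0.1617) = 369. Hazard ratio = 0.1763/0.2326 = 0.758.

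| f, r | Control incidence | Common effect: events, pooled HR | Power unstratified → stratified | No effect in previously infected: pooled HR, power |
|---|---|---|---|---|
| 20%, 0.2 | 25% | 452, 0.755 | 84.9% → 86.4% | 0.769, 80.1% |
| 20%, 0.5 | 27% | 485, 0.752 | 88.2% → 88.7% | 0.782, 77.9% |
| 40%, 0.2 | 21% | 369, 0.758 | 75.8% → 78.9% | 0.793, 61.5% |
| 40%, 0.5 | 25% | 436, 0.753 | 84.3% → 85.2% | 0.820, 55.8% |

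**4. Baseline-negative participants alone.** Events = (1 − f) × 535, which is 428 at f = 20% and 321 at f = 40%. At a hazard ratio of 0.75, power is 84.5% and 73.1%. If the previously infected get no benefit, this beats the pooled analysis in every row of the table. If the effect is common, the pooled analysis is better. That supports using it as a sensitivity analysis rather than as a replacement for the primary.

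**The case against.** The best case against acting is that this is a randomised trial. Prior infection should balance between arms on average, so its omission does not confound the comparison, and with a common effect the distortion is in the third decimal place. The covariate list is open-ended, so adjustment is not ruled out. Randomisation date is already in the model and absorbs part of any drift in the previously infected share. Section III also allows record review for predictors of COVID-19. All of this stands. It limits the size of the point without removing it. A date adjustment cannot separate an infected from a never-infected person enrolled on the same day, and an open list leaves the choice until after data are seen.

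Stronger readings are tempting, but the documents do not support them:

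- *The two sites would decide differently on the same person.* This is speculation. The itemised criteria carry no antibody rule, and antibody testing for both sites is done at UCM.
- *The sample size presumes a never-infected population.* The incidence comes from about 250 diagnoses among about 3,000 working staff over 4 months (250/3,000/4 ≈ 2% per month), raised to 3% and likened to the general local rate. Neither source is restricted to the never-infected.
- *The trial cannot report a result in never-infected people.* Antibodies are measured at intake, so such an analysis is possible but not prespecified.
- *Vaccination is not collected.* The survey contents are known only from a narrative summary. What can be verified is that vaccination is not a named covariate.

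A practical objection also stands. Section V allows either a nucleocapsid or a spike assay, and a spike result may reflect vaccination. Separate results for both proteins are stated only for UCM subjects under Aim 7. Baseline infection status is therefore not fully available from the intake antibody result alone.

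**Conclusion.** The wording conflict is certain and needs to be reconciled. The analysis gap is real and modest. Under the Section XVII rule, two groups likely to differ in risk are pooled, and the factor separating them is not prespecified.

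For an assumed 20–40% previously infected at 0.2–0.5 times the hazard, the consequence with a common effect is a pooled hazard ratio of 0.752–0.758 against 0.75 and a loss of about 0.5–3 points of power from not stratifying. If the previously infected get no benefit, the pooled hazard ratio is about 0.77–0.82 and power 56–80%. That pooled value is a fair average for those enrolled, but it dilutes the effect in the never-infected.

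A reader might infer that the trial is biased or its power claim wrong. Neither follows. The fall in events from 535 to 369–485 comes from who is enrolled and rests on the assumed share and hazard. No analysis choice recovers those events.

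**What to change.** 1. Reconcile the Section III Summary, the numbered criteria in Section VIII and the re-invitation bullet in Section XVII, so that one eligibility rule on prior infection and antibodies applies throughout.
2. In Section IX, prespecify baseline infection status as a stratification factor in the primary log-rank test and Cox model.
3. Prespecify the hazard ratio in baseline-negative participants as a sensitivity analysis. Stratification recovers the small power loss; only this analysis addresses dilution if the effect differs by infection history.
4. Define the status from the nucleocapsid result where available, plus any history of positive PCR recorded at screening. Do not count a spike-only positive as prior infection without vaccination information.
5. Restrict the seroconversion analysis to participants antibody-negative at baseline.
6. Add baseline vaccination as a named covariate if it is recorded.

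The cost is wording and a few lines of analysis code, with no added participants or visits. The drawbacks are some small strata and some participants whose status cannot be classified. The plan should say how the latter are handled, for example as a separate category.

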**2) Safety for higher dosing.** As stated above, there is strong evidence that safety risks up to 10,000 IU/d are minimal. Nevertheless, our study provides both frequent lab monitoring for side effects and education to enable subjects to recognize and respond to any symptoms of side effects if they occur. We also screen out participants with co-morbidities that predispose them to adverse outcomes from higher dose vitamin D supplementation. We have another vitamin D/COVID-19 study in progress with medically complex patients that will provide data on effectiveness and safety under intensive monitoring in that population.

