
administered to subjects post-randomization over the phone or via web-based survey at baseline, depending on subject preference, and every 3 months thereafter via a web-based instrument. Subjects will be given the option to call the study team and complete the survey over the phone in reminder emails. Survey and laboratory records will be maintained and monitored by study staff on encrypted, password-protected devices in compliance with UCM and RU IRB Information Security Office standards. Electronic Medical Records will be reviewed for predictors and indicators of COVID-19 and for severity of infection if subject has had a positive COVID-19 test result.

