## X. Potential risks and benefits to subjects

### Potential Risks

A potential risk of this intervention is vitamin D-mediated hypercalcemia. Given the exclusion criteria which screens for those at increased risk for developing hypercalcemia, this risk is anticipated to be low and will be monitored for throughout the intervention period via quarterly lab draws regularly reviewed by investigators, the DSMB, and the Clinical Advisory Committee. In addition, high doses of vitamin D have been associated with an increased risk of falls. Our exclusion criteria also attempts to minimize the likelihood of this risk by screening for those before enrollment at increased risk for developing this side effect. This risk will also be monitored in subject self-reports during survey administration. We believe this risk to be low in this study population. As with any study that involves blood draws, participants will also be exposed to the minimal risks of phlebotomy including pain, infection, and venous damage. These risks will be mitigated by using professionally trained phlebotomists. Since protected health information (PHI) is collected on web-based software, there is also a risk to loss of confidentiality, which we believe to be minimal. Precautions to minimize these risks are detailed below.

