### [Ensuring subject safety](#)

[figure not shown]
The proposed study will be supervised by PI and the Clinical Advisory Committee, with oversight by the DSMB and the University of Chicago Biological Sciences Division Institutional Review Board (UCM BSD IRB). All subjects will undergo written informed consent. Additional safety precautions include: 1) exclusion of individuals for whom higher dose vitamin D supplementation is more likely to be unsafe, 2) written materials on possible side effects of vitamin D supplementation provided at consent (i.e., risk of falls, symptoms of hypercalcemia), 3) monitoring of calcium levels to detect toxicity, 4) participants will be advised to report adverse events (email and study phone number provided), 5) independent testing of vitamin D supplements to ensure accurate potency, 6) rigorous infection control practices to mitigate the spread of COVID-19 at UChicago Medicine where testing is performed and 7) well-trained research staff.

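### No adverse event is planned to be tabulated by randomized dose, and no systematic collection of kidney stones or renal events is described

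*Combined protocol and SAP*

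**What the plan says.** **Definition.** The Section III Summary states: "Adverse events, defined as hypercalcemia or unexplained increased falls in either study arm will prompt discontinuation of the study medication". Section XII (Adverse Event Management) routes adverse events, serious adverse events and unanticipated problems to the DSMB at once, without defining any of the three.

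**Exclusions.** Section VIII excludes people who "Report a history of chronic kidney disease, including a history of abnormal GFR and/or creatinine" (criterion 2) or who "Report a history of kidney stones (1 in past year or 2 in lifetime" (criterion 7). Section III, on the safety of higher dosing, gives the purpose: "We also screen out participants with co-morbidities that predispose them to adverse outcomes from higher dose vitamin D supplementation". Section X (Potential Risks) links the exclusions to two named harms, hypercalcemia ("Given the exclusion criteria which screens for those at increased risk for developing hypercalcemia") and falls.

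**Collection.** Section XI lists "written materials on possible side effects of vitamin D supplementation provided at consent (i.e., risk of falls, symptoms of hypercalcemia" and says that "participants will be advised to report adverse events (email and study phone number provided". Section III (Procedures and Materials) says of the charts: "Electronic Medical Records will be reviewed for predictors and indicators of COVID-19 and for severity of infection". Tables 1-4 in Section IV apply a 12-month chart review to every cohort, with hospitalization and a positive COVID test as examples.

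**Analysis.** Section IX covers COVID-19 infection, seroconversion and disease severity. It contains no safety analysis.

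**The concern.** The trial compares 400 IU/day with doses 10 and 25 times as large (4,000/400 and 10,000/400). Section X (Potential Benefits) argues that, if the treatment works, its low risks and costs would encourage widespread use. That argument needs harms counted in the same way at each dose.

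For stones and renal events, the only description of collection is spontaneous or serious-event reporting. That depends on a participant seeing the event as reportable, and the written side-effect materials are described as covering falls and symptoms of hypercalcemia. Criterion 7 also admits a person whose only stone was more than a year ago, and nothing in Section VIII keeps that person out of the low-versus-high option on that ground. Recurrences could therefore occur at any of the three doses.

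Hypercalcemia and falls are monitored, but no comparison of them by dose is specified either. A final report that follows Section IX could say nothing about these harms by dose, and readers could take that silence as absence of harm.

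**Working it through.** The documents state no figure on this point, so the main check sets the sections side by side.

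| Event | In the Section III definition | Systematic collection described | Comparison by randomized dose planned |
|---|---|---|---|
| Hypercalcemia | Yes | Calcium at every draw (Sections III and XI) | None in Section IX |
| Falls | Yes | Self-report in surveys (Section X), though the survey description in Section III lists no falls item | None |
| Kidney stones | No | None described | None |
| Renal events | No | None described; no creatinine, GFR or urine test among the labs | None |

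The nearest thing to a safety comparison is in Table 5 of Section IV. The DSMB reviews baseline characteristics by arm (August 2021) and longitudinal testing data by arm (December 2021). The second presumably includes calcium. It is a review by arm, not by the three doses, and neither entry specifies a table of adverse events. Section XII has the DSMB review adverse events quarterly, with no split by arm or dose stated.

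**Size of what could be counted.** The inputs are:
- 1,000 low-dose participants: half of 2,000 (Section VII).
- Time on treatment: up to 9 months, with some cohorts at 3-6 months (Sections III and IV). I use 0.5 and 0.75 years.
- Stone rate: 0.3%, 0.5% and 1.0% per person-year. This is an assumption. The documents give no rate, and the exclusions could push the true rate down.
- Effect: a doubling, also an assumption.

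Expected control events = 1,000 × rate × years. Power is for a two-sided Fisher exact test at 0.05, 1,000 v 1,000, by exact summation over the two binomial distributions.

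| Years | Rate per year | Control events | Events if doubled | Power |
|---|---|---|---|---|
| 0.5 | 0.3% | 1.5 | 3 | 2% |
| 0.5 | 0.5% | 2.5 | 5 | 7% |
| 0.5 | 1.0% | 5 | 10 | 18% |
| 0.75 | 0.3% | 2.25 | 4.5 | 6% |
| 0.75 | 0.5% | 3.75 | 7.5 | 12% |
| 0.75 | 1.0% | 7.5 | 15 | 28% |

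Adding the 12-month chart review (0.75 + 1 = 1.75 years) gives 5.25-17.5 control events. Power is then 19-64%, but only if the doubling persisted for a year after treatment stopped.

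Systematic counting would also give a usable bound. With no events among 1,000 people, the one-sided 95% upper limit is 1 − 0.05^(1/1000) = 0.30%. For a dose group of 500, an assumed size, it is 1 − 0.05^(1/500) = 0.60%. Neither bound is available when events arrive only as spontaneous reports.

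**The case against.** The strongest reply is that these events are not shut out. Participants are told to report adverse events and are given contact routes. Section XII sends adverse events, serious adverse events and unanticipated problems to the DSMB, and its wording is not limited to two event types. The Section III sentence can also be read as listing only the events that stop study medication. All of this stands. A reader might infer from that sentence that stones and renal events would never be counted, but the documents do not support that. What remains is that no systematic collection is described and no table by dose is specified. If the sentence is only a stopping trigger, the protocol has no adverse-event definition at all, and the two sections still need reconciling.

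A reader might also infer that the plan names renal harm as a known effect of higher doses. It does not. It treats stones and kidney disease as histories that predispose to harm, and Section X explains the exclusions by hypercalcemia and falls. That they may also be outcomes of dosing is an inference.

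The survey evidence has a limit. Section III's account of the surveys omits falls, which Section X says are surveyed, so that account is not complete. The instrument is not in the documents, and the referral algorithms are figures not shown. A renal item may exist, and the sponsor should confirm. Chart review already covers all subjects, so only its fields need extending.

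Finally, the stone rate is assumed and the power is low. Both are true, which is why the case rests on description and not on a test.

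**Conclusion.** The point holds as a gap in collection and reporting. One narrow definition stands beside undefined terms in Section XII, and no systematic collection of stones or renal events is described. Section IX plans no tabulation of any adverse event by randomized dose. The wider part of the gap is that last item, since it also covers hypercalcemia and falls, the two harms the plan itself names. As written, the trial could not support a by-dose statement of low risk for these events.

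The gain from closing the gap is modest: about 1.5-7.5 stones per 1,000 controls over 6-9 months, and 2-28% power for a doubling. These figures rest on an assumed 0.3-1.0% per year, full enrollment of 1,000 controls, and 6-9 months on treatment for everyone. Cohorts treated for as little as 3 months would lower them. No figure is offered for kidney injury or new kidney disease. The finding does not show that higher doses harm the kidney or that the eligibility criteria are wrong. This is an inexpensive improvement that should be made; it does not put the primary analysis in doubt.

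**What to change.** 1. Reconcile the Section III Summary with Section XII. State one definition each of adverse event and serious adverse event, and keep it separate from the list of events that prompt discontinuation. Leave the discontinuation rule as it is.
2. Add one yes/no/date item on kidney stones and new kidney problems to the existing follow-up surveys, and confirm that a falls item is there.
3. Add these diagnoses to the fields of the 12-month chart review already planned for all subjects.
4. Add to Section IX a table of hypercalcemia, falls, stones and renal events by assigned dose (400, 4,000 and 10,000 IU). Show it within each randomization choice, because participants choose between the low-versus-moderate and low-versus-high options and only the comparison inside each option is randomized. Give exact confidence intervals, and include the table in the closed DSMB reports and the final report.

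The cost is protocol wording, one survey question, a few abstraction fields and one table. The downsides are slightly more abstraction work and wide intervals. No change to eligibility, dose or stopping rules is proposed.
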